**NU Study Number: NU 15B01**

**Other Study Number: MedImmune # ESR-14-10694 (D4190C00030)**

further investigational product if any of the following occurs for the subject in question:

- Patient voluntarily withdraws from treatment (follow-up observation is permitted)
- Patient is unable to comply with protocol requirements
- Patient experiences Grade  $\geq 3$  infusion reaction
- Patient experiences an adverse event that, in the opinion of the investigator or the sponsor, contraindicates further dosing
- Subject is determined to have met one or more of the exclusion criteria for study participation at study entry and continuing investigational therapy might constitute a safety risk
- Treating physician determines that continuation on the study would not be in the patient's best interest
- Patient becomes pregnant or intends to become pregnant
- Patient develops a second malignancy that requires treatment which would interfere with this study

Patients will not receive any further investigational product or further study observation if any of the following occurs for the subject in question:

- Patient becomes lost to follow-up (LTf)
- Patient withdraws consent
- Patient initiates an alternative anticancer therapy including another investigational agent

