Diagnosis & Key Eligibility Criteria	Patients must have a histologically documented (either primary or metastatic site) diagnosis of breast cancer that is HER2 negative (expansion cohort only TNBC allowed). Patients must have stage IV disease and must have completed at least one line of chemotherapy. Only TNBC patients will be enrolled in the expansion cohort. Also, only PD-L1 negative patients in the front line setting will be enrolled. Beyond frontline setting, any PD-L1 status is acceptable. . Patients must be ECOG performance status of 2 or less and have normal organ function. Patients treated with previous immunotherapies are excluded.
Treatment Plan	Patients will be treated with durvalumab 1500mg intravenously (IV) every 4 weeks for a total of 4 doses, and tremelimumab 75mg IV every 4 weeks for a total of 4 doses. After completion of the 4 doses of combination therapy, durvalumab will be continued at a dose of 750mg every 2 weeks for up to 18 additional doses, or until progressive disease or unacceptable toxicity. The first 750mg dose of durvalumab will be 4 weeks after the last combination dose. Patients will be followed for 3 years for survival and progression of disease.

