**4.0 TREATMENT PLAN**

**4.1 Overview**

Non-randomized, open-label, pilot phase II clinical trial of durvalumab in combination with tremelimumab in patients with stage IV HER2 negative breast cancer, with an expansion cohort of TNBC.

Patients will be treated durvalumab 1500mg intravenously (IV) every 4 weeks for a total of 4 doses, and tremelimumab 75mg IV every 4 weeks for a total of 4 doses. After completion of the 4 doses of combination therapy (induction phase), durvalumab will be continued at a dose of 750mg every 2 weeks for up to 18 additional doses (maintenance phase), or until progressive disease (see 4.1.1) or unacceptable toxicity. The first 750mg dose of durvalumab will be 4 weeks after the last combination dose. Patients may continue on therapy after progression or after initial 52 week treatment period as specified in Sections 4.1.1 and 4.1.2. Patients will be followed for 3 years or until time of death. Overall response rate (ORR), clinical benefit rate, PFS, and OS will be determined. In addition, patient's next line of therapy will be monitored for response rates and duration of clinical benefit to next line therapy.

Patients will undergo a fresh tissue biopsy prior to study enrollment and two months after treatment, unless deemed to be clinically inappropriate per PI or co-investigator, to evaluate pharmacodynamic changes in immune-related biomarkers. Correlatives will be assessed.

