#### 4.7 Duration of Follow Up

After patients come off treatment they will be followed up at 3, 6, 9, 12 months and then every 6 months for 3 years for survival and progression of disease.

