#### 4.8 Removal of Subjects from Study Treatment and/or Study as a Whole

Patients can be taken off the study treatment and/or study as a whole at any time at their own request, or they may be withdrawn at the discretion of the investigator for safety, behavioral or administrative reasons. The reason(s) for discontinuation must be clearly documented on the appropriate eCRF. In general, patients who are permanently discontinued from receiving investigational product will be followed for disease progression, survival, and safety, including the collection of any protocol-specified blood specimens, unless consent is withdrawn or the subject is lost to follow-up or administered subsequent therapy (see below). Subjects who decline to return to the site for evaluations will be offered follow-up by phone every 3 months as an alternative.

Patients will be permanently discontinued from study treatment and will not receive any

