 Thyroid function tests will include thyroid stimulating hormone, free T3, and free T4. During combination therapy, these labs should be monitored prior to each dose; during maintenance monotherapy, labs should be monitored every 8 weeks.

 Patients will be followed by routine clinic visit or phone call at 3, 6, 9, 12 months and then every 6 months for 3 years total from the end of treatment to document survival and disease progression.

 The maximum time interval between Screening Visit/ baseline study procedures and the first dose of study drug will be 14 days. Systemic imaging (CTs, bone scan or PET-CT) and consent may be performed up to 28 days prior. Note: Bone scans will be done only if the patient has bone disease. PET-CT is acceptable in place of bone scan, if a bone scan is contra-indicated for a patient's disease. The same modality used at baseline should be used throughout.

 Full physical examinations will include assessments of the head, eyes, ears, nose, and throat and the respiratory, cardiovascular, GI, urogenital, musculoskeletal, neurological, dermatological, hematologic/lymphatic, and endocrine systems. Height will be measured at screening only. Targeted physical examinations are to be utilized by the Investigator on the basis of clinical observations and symptomatology. Situations in which physical examination results should be reported as AEs are described in Section 10

 Resting 12-lead ECGs (x2, 5 minutes [+/- 2 min] apart) will be recorded at screening and as clinically indicated throughout the study. ECGs should be obtained after the patient has been in a supine position for 5 minutes and recorded while the patient remains in that position. At Screening, 2 ECG's will be obtained on which QTcF must be  $< 470$  ms. In case of clinically significant ECG abnormalities, including a QTcF value  $> 470$  ms, 2 additional 12-lead ECGs should be obtained over a brief period (eg, 30 minutes) to confirm the finding.

- 12 Vital signs (blood pressure [BP], pulse, temperature) will be evaluated according to the assessment schedules outlined in Section 4.2.1).
- 13 Hepatitis A antibody, hepatitis B surface antigen, hepatitis C antibody
- 14 80 mL of whole blood should be collected in eight 10 mL plastic lavender top tubes (K2EDTA)

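### Section 4.8 ends follow-up, survival included, once another anticancer therapy starts; this contradicts the 3-year follow-up and the next-line objective, and nothing says which governs

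*Combined protocol and SAP*

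**What the plan says.** **Section 4.8.** The opening paragraph says that patients permanently off study drug "will be followed for disease progression, survival, and safety", and then makes an exception: "unless consent is withdrawn or the subject is lost to follow-up or administered subsequent therapy (see below"). Two lists follow. The first ends study drug only, and its first item notes that observation may go on. The second is introduced by "Patients will not receive any further investigational product or further study observation if any of the following occurs for the subject in question", and contains three events: loss to follow-up, withdrawal of consent, and "Patient initiates an alternative anticancer therapy including another investigational agent".

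**Follow-up duration elsewhere.**
- Study Summary: "Patients will be followed for 3 years for survival and progression of disease".
- Section 4.1: "Patients will be followed for 3 years or until time of death".
- Section 4.7: after treatment ends, "they will be followed up at 3, 6, 9, 12 months and then every 6 months for 3 years for survival and progression of disease".
- Section 5.0, footnote 8: contact by clinic visit or phone, "for 3 years total from the end of treatment to document survival and disease progression".

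None of these makes an exception for new therapy.

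**Next-line data.** Section 4.1, objective 2.3.2, Section 6.4, the concomitant-medication row of the Section 5.0 table and Section 10.3 all plan to record response to the next line of therapy, its duration, or both. Section 10.3 runs that duration to the last dose of the next line.

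**Analysis.** OS is death from any cause (Sections 2.2.1 and 10.3). For patients alive at data cut-off, Section 10.3 censors OS at the date last known alive and PFS at the last tumour assessment. It does not mention new anticancer therapy for either endpoint.

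**The concern.** One event, the start of another anticancer therapy, ends observation under Section 4.8. Elsewhere it is the event after which required follow-up and planned data collection take place. Site staff cannot comply with both.

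Two things are at stake. First, a patient who leaves observation at next-line therapy contributes no later death to OS. Starting next-line therapy depends on progression and on fitness for more treatment, both of which are related to the risk of death, so the independent-censoring assumption behind the Kaplan-Meier estimate fails. If some staff follow 4.8 and others 4.7, the extent of OS follow-up also differs between patients for reasons the analysis does not record. Second, the next-line objective asks for data that 4.8, read as written, does not allow to be collected.

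**Working it through.** **1. Text comparison.** The point rests on this step; there is no figure in the plan to reproduce.

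| Item after new therapy starts | Section 4.8 | Other sections |
|---|---|---|
| Survival follow-up | Ends | Continues 3 years or to death (Summary, 4.1, 4.7, footnote 8) |
| Progression follow-up | Ends | Continues 3 years (Summary, 4.7, footnote 8) |
| Adverse event recording | Ends, as part of safety follow-up | 90 days after last dose (7.1, 7.3.3.5) |
| Next-line response and duration | Outside permitted observation | Planned (2.3.2, 4.1, 5.0 table, 6.4, 10.3) |

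Section 7.3.3.4 does have a stop at alternative therapy, but only for reporting serious adverse events to the manufacturer. No section states which rule takes precedence, or limits the 4.8 stop to scans or safety.

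**2. Consequence for OS.** If observation stops at new therapy, the date last known alive is about the date that therapy starts. The Section 10.3 rule then censors OS there, although Section 10.3 never says that OS should be censored at new therapy.

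**3. Illustrative size.** The documents give no next-line uptake, PFS, OS, gap to next-line therapy, or post-progression risk. All of the following inputs are assumptions:
- time to progression T1 is exponential, with median 2, 3, 4 or 6 months;
- post-progression survival T2 is exponential, scaled so that OS = T1 + T2 has median 9 or 12 months;
- 20, 40, 60 or 80% of patients are next-line candidates;
- the post-progression hazard in non-candidates is 1, 2 or 3 times that of candidates;
- candidates still alive are censored at T1 + 1 month; everyone else is followed to 36 months.

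This gives 4 × 2 × 4 × 3 = 96 scenarios, each with 200,000 simulated patients.

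| Next-line uptake | Patients with an observed death |
|---|---|
| 20% | 75-84% |
| 40% | 58-71% |
| 60% | 41-57% |
| 80% | 24-44% |
| Full follow-up, any uptake | 88-99% |

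The Kaplan-Meier median OS runs from 8.0 to about 15.4 months when the true median is 9, and from 9.8 to about 20.2 when it is 12. The shift in 12-month OS by assumed median PFS is:
- 2 months: -0.12 to +0.11
- 3 months: -0.05 to +0.18
- 4 months: -0.02 to +0.22
- 6 months: essentially zero to +0.23

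Downward shifts appear only when patients without next-line therapy have the higher risk. They are clear at short PFS and fade to nothing at 6 months.

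**4. What the documents hint about PFS.** In the Section 1.7.3 table, progression was the best response in 11/18 = 61% of patients overall and in 2/7 = 29% with triple-negative disease; one of those two was still on study at 10 months. This is best response in few patients, not a PFS estimate. It does not choose between the short and the longer PFS scenarios.

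**The case against.** **The intent can be recovered.** Four places on follow-up and five on next-line data point one way, and 4.8 stands alone. Appendix E shows that 4.8 was revised at Amendment 3 and next-line monitoring was added at Amendment 6, so 4.8 looks like an older paragraph that was not harmonised. That stands. It makes this an internal inconsistency rather than a deliberate design choice, but it does not remove the conflicting instruction.

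**Survival is named only in the lead-in.** That sentence opens with a general qualifier, and the list itself speaks only of study observation. This is correct. Applying the exception to survival is still the natural reading, and the list has no qualifier.

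**The next-line objective already relies on outside data.** It covers only patients able to submit data, and Section 10.3 accepts outside radiology reports. Collecting those reports is still observation after new therapy.

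**The simulation settles little.** Every input is assumed, and the grid is not a probability distribution. In about half of the scenarios the 12-month shift is below 0.05. With 20 to 28 patients and an assumed OS of 0.4, the sampling standard error alone is √(0.4 × 0.6 / 28) = 0.09 to √(0.4 × 0.6 / 20) = 0.11. The model also has every patient progress before death, which may overstate how many reach the trigger. All of this stands, and the ranges are offered as illustration only.

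**Stronger readings.** A reader might infer that the plan censors OS at new therapy, that survival follow-up was in fact stopped, or that reported OS will be too high. The documents support none of these. Section 10.3 has no such censoring rule, nothing shows which section staff followed, and the bias can go either way.

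**Conclusion.** The contradiction is real and rests on the text alone. Section 4.8 ends survival and all other study observation at new anticancer therapy, the follow-up sections and the next-line objective require observation to continue, and nothing sets precedence.

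The statistical consequence is conditional. Where 4.8 is followed, OS censoring is informative and the next-line objective falls outside permitted observation. The documents fix neither the sign nor the size of the OS bias; the range of -0.12 to +0.23 at 12 months depends wholly on the assumptions above.

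The reach is limited. Response rate, the primary endpoint, is largely unaffected. OS is secondary with no stated hypothesis, and next-line response is exploratory. Appendix E (Amendment 12) records closure on 7.20.2020 for low accrual, so the benefit is confined to patients still in follow-up, whose number is not given, and to how OS is reported. Priority is minor to moderate.

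**What to change.** - **Section 4.8.** Leave the study-drug part of the item as written. State that starting another anticancer therapy does not end survival follow-up or next-line data collection, both of which continue at the visits or calls already planned until death, withdrawal of consent, loss to follow-up or 3 years. Take survival out of the lead-in exception.
- **Section 10.3.** State that OS is not censored at new therapy, and state how PFS is handled at new therapy.
- **Remaining conflicts.** Reconcile the rest of 4.8 with the progression follow-up in the Study Summary, Section 4.7 and footnote 8, and with the 90-day adverse event recording in Sections 7.1 and 7.3.3.5. Which rule should apply there is for the investigators to decide.
- **Optional.** Extend the next-line row of the Section 5.0 table beyond the 3-month contact, where it now stops, to later contacts already in the schedule.

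The survival and next-line changes cost protocol wording and a few more data items (vital status, next-line regimen and start date, best response, last-dose date), by phone if needed. They add no scan, blood sample or visit. Any cost of the reconciled progression and safety rules depends on what is chosen.

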#### **4.9 Patient Replacement**

If a patient is enrolled in the study but comes off study before cycle 1 day 1 of treatment, the patient may be replaced.

A patient who does not reach the first imaging assessment at 2 months for reasons other than clinical progression will not be used toward assessment of the primary clinical endpoint (ORR), PFS or OS. However, they will be included in the final safety analysis. Additional patients may be added if needed for assessment of response.

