### **2.2 Secondary Objectives & Endpoints**

2.2.1 To evaluate PFS and OS in patients with metastatic HER2 negative breast cancer treated with durvalumab in combination with tremelimumab.

Secondary endpoints include PFS and OS, where PFS is defined as the time from date of treatment initiation to date of documented disease progression or death (by any cause in the absence of progression), and OS is defined as the time from date of treatment initiation until death due to any cause.

2.2.2 To evaluate safety and tolerability.

The endpoints will be the number, frequency, and severity of adverse events (as defined by the NCI Common Terminology Criteria for Adverse Events or CTCAE version 4.03) will be recorded.

2.2.3 To evaluate clinical benefit rate in this population.

Clinical benefit rate is defined as stable disease (SD) for  $\geq$  12 weeks + PR + CR.

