### 6.3 Secondary Endpoints

Secondary endpoints include PFS and OS, where PFS is defined as the time from date of treatment initiation until date of documented disease progression or death (by any cause

in the absence of progression), and OS is defined as the time from date of treatment initiation until death due to any cause.

Clinical benefit rate will be assessed and defined as SD (for  $\geq$  12 weeks) + PR + CR. Any patient who has completed two months of study therapy is evaluable for this end point

The number, frequency, and severity of adverse events (as defined by the NCI Common Terminology Criteria for Adverse Events or CTCAE version 4.03) will be recorded. Any patient treated with minimum 1 dose of either study drug will be evaluable for toxicity.

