#### **7.2.5.5 Gastrointestinal disorders**

**Diarrhea/colitis:** is the most commonly observed treatment emergent SAE when tremelimumab is used as monotherapy, but may also be related to durvalumab. In rare cases, colon perforation may occur that requires surgery (colectomy) or can lead to a fatal outcome if not properly managed. There were no CTC Grade 4 or 5 events from the pooled dataset, however, fatal events of colitis have been reported with durvalumab in combination with tremelimumab. Guidelines on management of diarrhea and colitis in patients receiving tremelimumab are provided in Table 1.

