#### **Myositis/polymyositis**

In the durvalumab pool of studies as of the DCO, 3 patients (0.2%) reported the event of myositis, including 1 CTCAE Grade 3 in severity. Outside of the pooled dataset, there were 2 fatal events of polymyositis considered as treatment-related by the Investigator.

In the durvalumab + tremelimumab combination pool, Grade 3 myositis event were reported in 1 patient (<0.1%). In addition, there were 4 SAEs of myositis reported from studies outside of the pooled dataset. Grade 2 polymyositis was reported in 1 patient (<0.1%) from the combination pooled dataset and 2 additional patients (1 each retrieved from the global safety database and a study outside of the pooled dataset). The severity of these events were Grade 3 and Grade 5 with the latter patient having died due to the event of polymyositis which was considered related by the Investigator. Autopsy showed polymyositis involving the diaphragm and chest wall muscles.

Investigators should adhere to the Toxicity Management Guidelines by performing a thorough evaluation to rule out alternative aetiologies and initiating prompt treatment with steroids and modification of study drug dose regimen depending on the severity of the event. Refer to the Toxicity Management Guidelines.

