#### **10.3**

#### **Data Analyses Plans**

The primary analysis will be on the intent-to-treat (ITT) population, including all evaluable patients. Best ORR defined as will be defined as number (%) of patients with at least one visit response of complete or partial response by the Response Evaluation Criteria in Solid Tumors (RECIST 1.1). Best objective response prior to disease progression will be used. The overall response rate will be estimated by the proportion of overall response, and its 80% confidence interval (CI) and 95% CI will be estimated using the exact binomial distribution.

Additionally, we will evaluate clinical benefit rate, defined as stable disease for  $\geq 12$  weeks complete or partial response using RECIST 1.1 guidelines in a similar manner. We will also perform similar analyses using Immune Related RECIST (irRECIST).

PFS is defined as the time from date of treatment initiation until date of documented disease progression or death (by any cause in the absence of progression). OS is defined as the time from the date of start of treatment until death due to any cause. For patients alive at the time of data cut-off, PFS and OS will be censored as of the last tumor assessment date or known to be alive, respectively. The PFS and OS will be estimated using the Kaplan-Meier method. The number, frequency, and severity of adverse events (as defined by the NCI Common Terminology Criteria for Adverse Events or CTCAE version 4.03) will be recorded.

Baseline percent PDL1 expression, TILs (sTILs, iTILs, and their ratio), and changes in T cell subpopulations will be used as a continuous variable to predict clinical benefit or overall response rates using appropriate statistical summaries. Cox proportional hazards regression will be used to compare how these biomarkers are associated with PFS and OS as well.

Changes from baseline in these biomarkers will also be analyzed to assess for pharmacodynamic effects of treatment. Continuous variables will be analyzed using either paired t-tests, signed rank tests or repeated measures analysis of variance.

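### Section 4.9 drops early deaths not due to progression from PFS and OS, although both endpoints are defined to count death from any cause

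*Combined protocol and SAP*

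**What the plan says.** Section 4.9 (Patient Replacement) deals first with patients who leave before Cycle 1 Day 1, who may be replaced. It then says that anyone lacking the 2-month scan "for reasons other than clinical progression will not be used toward assessment of the primary clinical endpoint (ORR), PFS or OS". These patients stay in the safety analysis, so the rule reaches people who have been treated. Extra patients may be added for the response assessment.

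The endpoint definitions carry no such restriction. Section 2.2.1 says "OS is defined as the time from date of treatment initiation until death due to any cause". Section 6.3 says "PFS is defined as the time from date of treatment initiation until date of documented disease progression or death (by any cause", and continues with the condition that progression has not occurred first. Sections 10.1 and 10.3 define both endpoints in the same way.

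On analysis sets, section 10.3 says "The primary analysis will be on the intent-to-treat (ITT) population, including all evaluable patients". It names no separate set for PFS and OS. Its censoring rule begins "For patients alive at the time of data cut-off, PFS and OS will be censored as of the last tumor assessment date" and gives the date last known alive as the counterpart for OS.

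**The concern.** The only exception in 4.9 is clinical progression. A patient who dies in the first two months from treatment toxicity or an unrelated illness misses the scan for another reason and so leaves the PFS and OS sets. For that patient the endpoint event is what triggers the exclusion. Inclusion then depends on what happened after time zero, while follow-up time is still counted from time zero.

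The protocol's own safety text shows that such a death is possible. Section 7.2.5.5 notes that "fatal events of colitis have been reported with durvalumab in combination with tremelimumab". The Myositis/polymyositis text describes a combination-treated case with "the latter patient having died due to the event of polymyositis which was considered related by the Investigator". The Myocarditis text records two fatal cases with the combination: one was judged unrelated, and in the other the patient was also receiving chemotherapy.

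The reported PFS and OS would be too favourable and would not match their stated definitions. The deaths would appear only in the safety tables.

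**Working it through.** **Reading the sections together**

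1. 2.2.1, 6.3, 10.1 and 10.3: time zero is the start of treatment, and death from any cause is an event for OS and, absent progression, for PFS.
2. 4.9: no 2-month scan for a non-progression reason means the patient is not used for PFS or OS.
3. 10.3: the population sentence concerns the primary analysis and is itself limited to evaluable patients. The censoring sentence covers only patients alive at cut-off. Neither returns a patient who died before the scan.
4. An analyst who follows the plan must therefore delete an event that the definitions count.

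**Effect of a deletion**

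The plan states no PFS or OS figure, event count or early-death count, so there is nothing to reproduce.

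- n = patients retained: 20 (planned evaluable, expansion cohort, section 3.0) or 28 (planned evaluable, general cohort, section 10.2).
- k = early non-progression deaths deleted: an assumption, shown for 0, 1 and 2.

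Without censoring before time x, the Kaplan-Meier estimate is the number still event-free at x divided by the number at the start. Let a be the number still event-free. Then:

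- with deaths deleted: a/n
- with deaths restored: a/(n+k)
- ratio, deleted to restored: (n+k)/n

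After the last early death the two risk sets are identical, so the ratio stays constant even if there is censoring later.

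| n | k | (n+k)/n | A reported 70% becomes |
|---|---|---|---|
| 20 | 0 | 1.000 | 70.0% |
| 20 | 1 | 21/20 = 1.050 | 70/1.050 = 66.7% |
| 20 | 2 | 22/20 = 1.100 | 70/1.100 = 63.6% |
| 28 | 0 | 1.000 | 70.0% |
| 28 | 1 | 29/28 = 1.036 | 70/1.0357 = 67.6% |
| 28 | 2 | 30/28 = 1.071 | 70/1.0714 = 65.3% |

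The 70% is illustrative. A numerical check, which added k deaths between months 0.2 and 1.8 and compared Kaplan-Meier estimates at 6 months, gave the same ratios.

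At 8 weeks, with no other event by then, 4.9 would report 100%. With one death restored the value is 20/21 = 95.2% in the expansion cohort. With 30 treated in the general cohort it is 29/30 = 96.7% for one death and 28/30 = 93.3% for two.

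**How large k might be**

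The intestinal perforation text in 7.2.5.5 describes 2 deaths in a pool of 1,088 combination patients: 2/1,088 = 0.18%. Both were judged unrelated, and one was attributed to progression as well. That rate gives 20 × 2/1,088 = 0.04 expected deaths in 20 patients and 28 × 2/1,088 = 0.05 in 28. It covers one cause, at any time on study, so it does not bound k.

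**Patients who leave early and do not die**

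- PFS: with no post-baseline scan, progression or death, a patient adds no information whether excluded or censored at Day 1. Adding such a patient left the curve unchanged (0.267 both ways).
- OS: the direction is undetermined. Take 20 retained at 70% and 2 leavers with survival s. The full-set value is (20 × 0.70 + 2s)/22, which is 67.3% for s = 40%, 70.0% for s = 70% and 71.8% for s = 90%.

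The point is therefore confined to early deaths.

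**The case against.** The strongest reply is that 4.9 is a replacement clause in the treatment section, and that the statistical sections set no evaluability limit for PFS or OS. The population sentence in 10.3 is about the primary analysis, which is ORR. On that reading this is a gap to reconcile. The observation about 10.3 is right, but it does not help: 4.9 names PFS and OS explicitly, and silence elsewhere does not override it.

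A second reply concerns size. The number of early deaths is unknown. None of the fatal cases in section 7 has a time of death, so none is shown to fall before week 8, and the one rate with a denominator implies far fewer than one expected death. Clinical progression is also not defined, so a death with progression as a contributing cause might be kept. This stands. The effect may be zero, and k = 2 is only an illustration. Whether a death was judged treatment-related does not matter for an any-cause endpoint.

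Third, PFS and OS carry no hypothesis or threshold, and the deaths remain visible in the safety analysis. That limits the seriousness, but the reported curves would still be wrong for any k above zero.

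Finally, Appendix E records that the study closed in July 2020 for low accrual, so n = 20 may not describe the analysed cohort. If fewer patients were analysed, each deleted death would weigh more.

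**Conclusion.** The concern holds. As written, 4.9 deletes from PFS and OS an event that both definitions count, and no other section reverses it. For deaths the direction is fixed: later estimates are inflated by (n+k)/n, which is 5.0% per death at n = 20 and about 3.6% per death at n = 28. This assumes no censoring before the early deaths. The size depends on k, which the documents do not give; zero or one would not be surprising in cohorts this small. No direction is claimed for OS in early leavers who did not die.

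The matter deserves correction but does not undermine the main result. Correcting PFS and OS leaves the two-stage rule and the 8-of-20 Bayesian criterion for ORR as they are. The same sentence in 4.9 also removes these patients from ORR; that is a separate question, not assessed here.

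**What to change.** - In 4.9, remove PFS and OS from the exclusion.
- In 10.3, state that PFS and OS are analysed in every patient who received at least one dose of either study drug. Section 6.3 already uses this set for toxicity.
- Count any death before the first scan as an event for both endpoints.
- For patients without progression or death, censor PFS at the last tumor assessment, or at Day 1 if there is none after baseline. The Day 1 rule is needed because, under section 5.0, "Systemic imaging (CTs, bone scan or PET-CT) and consent may be performed up to 28 days prior", so censoring at the baseline scan could give zero or negative time. Censor OS at the date last known alive.
- Report how many patients this restores and why each missed the scan. The evaluable-only version can be kept as a sensitivity analysis.

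The cost is wording in two sections, with no new visits or samples. Section 4.8 already provides, in general, for survival follow-up after treatment stops. Some restored patients will have short OS follow-up, because observation ends at consent withdrawal, loss to follow-up or new anticancer therapy. The reported PFS and OS may be slightly less favourable.
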